	
Optimal dosage and conditions, as well as possible mechanisms of action for IH remain unclear. Adequately powered randomized, controlled trials are required to confirm whether IH is viable as a longer-term treatment option for obesity and the associated comorbidities.
 
This proposed novel research addresses functional and medical concerns following SCI. The purpose of this proposal is to examine changes in glycemic control and metabolism while at rest and during exercise after 5 days of resting exposure to AIH when compared with a time-matched normoxia (SHAM) treatment.

5.	Inclusion and Exclusion Criteria
	
Screening: Subject candidates will be pre-screened by phone or personal contact to determine their eligibility based upon age and body habitus (i.e., height/weight). Subjects with SCI and non-injured control (CON) subjects will be recruited.
 
Inclusion Criteria:
 
 a. Males and females aged 18-60 years. b. SCI only: 
 1. Lower extremity weakness or paralysis at C5 or below resulting from spinal cord injury for at least one year. 2. ASIA Classification A-D c. Overweight or obese as classified by a Body Mass Index (BMI) (kg/m^2) of ≥ 25.0 (CON) and ≥ 22.0 (SCI). d. Resting $\text{SaO}_2 \geq 95\%$ 
Exclusion Criteria SCI and CON:
 
 a. Currently hospitalized b. Resting heart rate ≥ 120 BPM c. Resting systolic blood pressure > 180 mm Hg d. Resting diastolic Blood Pressure > 100 mmHg e. Self-reported history of unstable angina or myocardial infarction within the previous month f. Previous cardiac surgery or condition that evidences ischemic heart disease g. Cardiopulmonary complication such as COPD h. Pregnancy determined by urine testing in sexually active females.
6.	Number of Subjects
	Total target accrual is N= 20; 10 SCI and 10 CON.
7.	Study-Wide Recruitment Methods

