	
Subject candidates will be recruited by word-of-mouth, casual contact, online advertisement on The Miami Project to Cure Paralysis website and phone calls.
 
The Miami Project maintains a database of persons who have volunteered their participation in research studies. This is a searchable database under the management of [name]., Director of Education. The Miami Project also maintains a database of individuals who have participated in past studies and volunteered ongoing participation. These databases contain information such as age, date of injury and level of injury, and impairment scale score that will allow us to screen potential subjects. These individuals will be contacted via phone or email. As the target recruitment is 20 subjects, we are confident that this level of enrollment can be satisfied.

8. Study Timelines	 
The diagram illustrates the study timeline across four consecutive days (Day 1 to Day 4). It begins with 'Consent & review of medical inclusion/exclusion criteria' and a '30 min rest & GXT'. Days 1-4 are consecutive. On Day 1, participants undergo 'Day 1 OGTT - 75 g (fasted) AIH or SHAM Treatment'. On Days 2, 3, and 4, they receive 'AIH or SHAM Treatment'. Within 24 hours of the final exposure (Day 4), there is another '30 min rest & GXT'. Following this, there is a '3 week washout (for some participants; dependent on randomization order)'. Finally, participants repeat all testing with the treatment they did not receive.
 <pre>graph TD; A[Consent & review of medical inclusion/exclusion criteria 30 min rest & GXT] --> B[Days 1-4 are consecutive]; B --> C[Day 1 OGTT - 75 g (fasted) AIH or SHAM Treatment]; B --> D[Day 2 AIH or SHAM Treatment]; B --> E[Day 3 AIH or SHAM Treatment]; B --> F[Day 4 OGTT - 75 g (fasted) AIH or SHAM Treatment]; F --> G[Within 24 hours of final exposure 30 min rest & GXT]; G --> H[3 week washout (for some participants; dependent on randomization order)]; H --> I[Repeat all testing with treatment not received];</pre>

9.	Study Endpoints
	The study will end after 20 participants have completed all testing. For each subject the study will end after AIH and SHAM exposures and post-testing (resting and exercise assessments) have been completed.
10.	Procedures Involved

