
- j. any failure of the testing or recording equipment.

Without need for additional data collection we will calculate resting and whole body fat oxidation from ventilator data. Total energy expenditure (TEE), and whole body carbohydrate (CH_2O), and fat oxidation rates will be calculated using the following stoichiometric equations assuming negligible urinary nitrogen excretion rates:

$$\begin{aligned}\text{TEE (kcal/min)} &= 3.9 \text{ VCO}_2/\text{RER} + 1.11 \text{ VCO}_2 \\ \text{CH}_2\text{O oxidation (g/min)} &= 4.55 \text{ VCO}_2 - 3.219 \text{ VO}_2 \\ \text{Fat oxidation (g/min)} &= 1.67 \text{ VO}_2 - 1.67 \text{ VCO}_2\end{aligned}$$

where VCO_2 is the rate of carbon dioxide produced in L/min, RER is the respiratory exchange ratio (VCO_2/VO_2), and VO_2 is the rate of oxygen consumed in L/min. Rates of whole body CH_2O and fat oxidation will be converted to weight relative units ($\mu\text{mol}/\text{kg}\cdot\text{min}$) using the molecular weights of glucose (180 g/mol) and a representative TG (860 g/mol). Fat oxidation will be converted to fatty acid oxidation by multiplying by 3 (3 mol fatty acids/mol TG).

Ratings of perceived exertion (RPE) will be assessed using the Categorical-Ratio (1-10) scale of Borg. Subjects will be shown a laminated sheet containing descriptors of their perceived effort ranging from 'nothing at all' (0) to very, very hard (Maximal=10). Subjects will state the number that corresponds to their perception of the difficulty of their task with specific respect to: a) their arms and b) their effort of respiration.

Blood pressure will be measured by a calibrated ambulatory pressure monitor (A&D Engineering, Inc.) placed on the dominant arm.

For determination of lactate concentration, capillary blood will be sampled from the earlobe in the last 15 seconds of each 3 minute stage as well as 1, 3, 5 and 10 minutes after cessation of exercise. The earlobe will be prepared using alcohol swabs and will then be punctured with a lancet. Samples will be analyzed immediately using a precalibrated analyzer (Lactate Plus, Nova Biomedical, Waltham, MA)

3. Participants will be randomly assigned (by the flip of a coin) to receive both AIH or SHAM intervention and then the alternate intervention no less than 3 weeks later. The order of treatment will be randomly assigned and counterbalanced. Participants will be blinded to the intervention they are receiving. Intervention order will be stored in a password protected document.

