Participants will receive intermittent exposure to moderate hypoxia (AIH) (HYP-123; Hypoxico Inc, New York, NY) under resting conditions. IH treatment will take place over a period of 4 consecutive days involving daily (Monday-Friday,) hour long sessions of alternating 6-minute hypoxic intervals ($\text{FIO}_2 = 0.09-0.12$) with 3-minute normoxic intervals ($\text{FIO}_2 = 0.21$). During hypoxic intervals, oxygen concentration may be adjusted to maintain participants SpO_2 levels between 75-90% (as previously described in IRB approved protocol #20150117). SHAM protocol will be the same as described above with $\text{FIO}_2 = 0.21$ at all times.

Blood oxygen concentration (SpO_2) will be continuously monitored with a pulse oximeter to ensure that participants do not fall below 75%. The following will also be monitored during and after hypoxia treatments: headaches, pain, lightheadedness, dizziness, altered vision, respiratory distress, cyanosis, spasms, autonomic dysreflexia or change in function.

4. On day 1 and day 4 of each treatment series, subjects will undergo a fasted OGTT (as described below #5.). On day 1, the OGTT will be performed before the treatment and on day 4 it will be performed after the treatment. Each treatment series will be followed by a repeat of the graded exercise tests within 24 hours of the final exposure session as described in Section 10.3 of this document.

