Data – storage location - Data are stored in a locked room (LPLC 1-50), in a locked cabinet which is only accessible to study personnel in the Lois Pope Life Center, [name]. A security badge is needed to open the office door where the data is stored. A security guard is located in the front lobby and the hallway to the storage site secured by proximity card entry.

12. Data Management

Data Analysis

We will use a mixed-model ANOVA and a repeated measures design to examine main effects of *test condition* (AIH versus SHAM) and time. Post hoc analyses will use the Least Significant Difference test. Significance for all tests will be set *a priori* at $\alpha \leq 0.05$.

The outcomes being addressed have never been studied for this population and there are no data on which to empirically base study power. We will be using this study to obtain data necessary to compute effect sizes for future work.

Data will be analyzed using IBM SPSS Statistics (IBM Corp., Armonk, NY, USA) version 22.0 software.

Security, Confidentiality, Privacy

Security & Confidentiality

Please see section 26. Confidentiality – local procedures.

	
Privacy Please see section 27. Provisions to Protect the Privacy Interests of Subjects.

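### Treatment order is set by coin flip yet called counterbalanced, and no period term is named, so a period effect can bias or blur the AIH-SHAM estimate

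*Combined protocol and SAP*

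**What the plan says.** The study is a two-period crossover: every participant has one AIH series and one SHAM series, at least three weeks apart (section 10, item 3). The same item describes allocation in two ways. First: "Participants will be randomly assigned (by the flip of a coin) to receive both AIH or SHAM intervention". Two sentences later: "The order of treatment will be randomly assigned and counterbalanced". Nothing says how coin flips are made to balance. Section 6 gives the size: "Total target accrual is N= 20; 10 SCI and 10 CON".

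The analysis paragraph in section 12 reads: "We will use a mixed-model ANOVA and a repeated measures design to examine main effects of *test condition* (AIH versus SHAM) and time". Section 10 (Research Design) uses *time* as the repeated-measures factor, and neither place defines it as period. Section 12 also gives the purpose: "We will be using this study to obtain data necessary to compute effect sizes for future work".

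The two aims are measured differently (section 10, item 4). For glycaemia: "On day 1 and day 4 of each treatment series, subjects will undergo a fasted OGTT". For exercise and resting metabolism: "Each treatment series will be followed by a repeat of the graded exercise tests within 24 hours of the final exposure session". The only pre-treatment exercise test clearly described is the one at screening. For the second series the timeline in section 8 says only "Repeat all testing with treatment not received".

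**The concern.** In a two-period crossover, anything that shifts results between the first and second series, such as familiarity with the graded exercise test, is separated from treatment in one of two ways: by equal numbers in each order, or by a period term in the model. The protocol intends the first but gives a method that does not secure it, and it does not name the second.

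The exposure differs by outcome. If the single screening exercise test is the baseline for both series, it cancels and the contrast is simply post-AIH minus post-SHAM. An additive shift between series then stays in. The OGTT has its own day 1 test in each series, so an additive shift cancels from the day 1-to-day 4 change and only a period-by-time effect could remain.

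At stake is the product the study is meant to deliver: effect sizes for planning later trials. An unequal split moves the estimated difference; an equal split without a period term inflates the SD used to standardise it.

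**Working it through.** The plan gives no power, SD, effect size or balance probability, so there is no figure of its own to reproduce.

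**Inputs.** From the documents: N = 20 (10 SCI, 10 control), coin-flip order, alpha 0.05. Assumed: independent fair flips, a two-sided test, and a period effect *p* of 0.25, 0.5 or 1 within-subject SD. The SD of a paired difference is √2 within-subject SD. All SDs below are within-subject unless stated.

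**Chance of balance (exact binomial).**
- P(10:10) = C(20,10)/2^20 = 184,756/1,048,576 = 17.6%.
- P(5:5 in both groups) = (252/1,024)² = 0.246² = 6.1%.
- P(12:8 or better) = 73.7%; P(13:7 or worse) = 26.3%; P(14:6 or worse) = 11.5%.

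**Leakage with an unequal split.** Each AIH-minus-SHAM difference has expectation τ + *p* for SHAM-first participants and τ − *p* for AIH-first participants. The unadjusted mean therefore has expectation τ + *p* × (n_SHAM-first − n_AIH-first)/N. The share leaking is 4/20 = 0.2 at 12:8, 6/20 = 0.3 at 13:7 and 8/20 = 0.4 at 14:6. Averaged in absolute value over coin flips it is 0.18 for N = 20, and 0.25 within a group of 10.

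**Bias and type I error without a period term** (paired t-test; 200,000 simulated trials per setting):

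| Split | Bias (SD) at *p* = 0.25, 0.5, 1 | Type I error at *p* = 0.25, 0.5, 1 |
|---|---|---|
| 12:8 | 0.05, 0.10, 0.20 | 4.9%, 4.6%, 4.0% |
| 13:7 | 0.075, 0.15, 0.30 | 5.2%, 5.9%, 7.3% |
| 14:6 | 0.10, 0.20, 0.40 | 5.7%, 7.6%, 12.7% |

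With the period term, type I error is about 5% at every split. Without it, but averaged over coin flips, it is 5.0%, 4.9% and 5.0%.

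**Blur with an equal split.** At 10:10 the expected variance of the differences is 2 + *p*² × 20/19 instead of 2.
- The standardised effect shrinks by 1 − √(2/(2 + *p*² × 20/19)). For *p* = 1 this is 1 − √(2/3.053) = 19%; for 0.5 and 0.25 it is about 6% and 2%.
- A later sample size based on it is multiplied by (2 + *p*² × 20/19)/2 = 1.03, 1.13 and 1.53, that is, about 3%, 13% and 53% too large.
- Mean 95% CI half-width without the term: 0.66, 0.69 and 0.81 SD; with it, 0.655 SD.
- Power for an assumed 1 SD treatment effect: 84%, 82% and 71% without the term; 85% with it.

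**What each remedy does alone.** Forcing 10:10 removes the bias but leaves the blur. The period term removes both, but at 14:6 the half-width is 0.715 SD, against 0.655 at 10:10 (0.715/0.655 = 1.09, so 9% wider).

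**The case against.** The strongest case is that the text leaves room for a sound procedure. A coin could set the order for the first of each pair, with the second given the reverse; balance would then hold and 17.6% would not apply. *Time* might be coded as test occasion, which would carry period. The section 8 instruction to repeat the testing may include a fresh exercise test before the second series, in which case an additive shift would cancel there as it does for the OGTT. None of these is written down. Each would weaken the point if confirmed, and the third would reduce the contrast between the two aims.

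Second, coin-flip randomisation is valid. That stands in full: averaged over flips there is no bias and type I error is about 5%.

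Third, the size rests on an assumed period effect. That also stands. The larger figures need the top of the assumed range, and the 12.7% also needs a split at the 14:6 level. At 0.25 SD the consequences are slight, and 12:8 or better, which occurs 73.7% of the time, does not inflate type I error.

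Fourth, N is not fully settled: section 22 (Resources Available) gives a target of 6 per group. With 12 participants P(6:6) is 22.6%, so the conclusion is unchanged.

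Finally, a balanced list balances assignment, not completers. This is a reason to have the period term as well as the list.

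**Conclusion.** The concern holds. Followed as written, the plan does not secure the counterbalancing it states, and it names no term to absorb a period effect. The result is bias conditional on an unequal split, or lost precision and an understated standardised effect with an equal one. It is not a failure of randomisation.

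The balance probabilities are exact given 20 independent flips. The leakage shares are algebra. The type I error, power and effect-size figures depend on the assumed period effects. The exercise and resting outcomes of Aim 2 are the most exposed if there is no new baseline before the second series; the OGTT is exposed only to a period-by-time effect. Because the study exists to supply effect sizes and the remedy is nearly free, the change should be made.

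**What to change.** 1. **Add period** (first or second series) as a fixed effect for the exercise and resting outcomes. For the OGTT, include period in the model of the day 1-to-day 4 change, which is equivalent to period-by-time. This matters most, and it can still be specified before analysis if enrolment has begun.
2. **State one allocation method**: a computer-generated, concealed order list in permuted blocks, stratified by SCI/CON, giving 5 AIH-first and 5 SHAM-first in each group of 10. Keep the block sizes from staff who know earlier assignments.
3. **Clarify** whether the resting and graded exercise test is repeated before the second series, and what *time* denotes in the model.

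The cost is one list and one degree of freedom. At 10:10 with no period effect, the term widens the CI half-width only from 0.653 to 0.655 SD. No extra visits, staff or participants are needed.

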Effects of Acute Intermittent Hypoxia (AIH) on Metabolism, Dysglycemia, and Substrate Partitioning during Exercise

eProst Number: 20160818

Version Date: September 1, 2017

[figure not shown]
Version Number: 0.05

Principal Investigator Name: [name]

NCT Number: NCT02973438

	HRP-503 Template Protocol (7)
1. Protocol Title	Effects of Acute Intermittent Hypoxia (AIH) on Metabolism, Dysglycemia, and Substrate Partitioning during Exercise
2. IRB Review History	NA
3. Objectives	
Specific Aims
 
Specific Aim 1: Assess whether 4 days of exposure to AIH at rest in overweight or obese individuals with and without SCI will result in improved glycemic control when compared to a normoxic (SHAM) condition.
 
Specific Aim 2: Assess whether 4 days of exposure to AIH administered while at rest in overweight or obese individuals with and without SCI will result in a greater reliance on fat as a fuel source at rest and during exercise when compared to a normoxic (SHAM) condition.

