	We are not enrolling pregnant women, prisoners, persons under age 18, or cognitively impaired adults.
18.	Multi-Site Research
	NA
19.	Community-Based Participatory Research
	This project does not involve community based participatory research.
20.	Sharing of Results with Subjects
	Study outcomes for individual and group results will be shared with study participants upon completion of the study.
21.	Setting
	Procedures described in section 5. Procedures Involved will be completed in the Lois Pope Life Center on the Miller School of Medicine Medical Campus. Blood samples will be analyzed in the Clinical Biochemistry Lab or the DRI (3 rd Floor).
22.	Resources Available
	=Study Personnel =

[name] is a Professor in the in the Department of Neurological Surgery and Rehabilitation Medicine, and a Principal Investigator (Applied Physiology Research) for the Miami Project. He will serve as a Principal Investigator on the protocol and assessments, and will assist with data interpretation and dissemination.

[name], is an Associate Professor in the Department of Rehabilitation Medicine, who is boarded in Rehabilitation Medicine. He will conduct physician evaluations of study subjects and be notified of any (S)AEs. He will be responsible for all medical aspects of the study, injuries, and participant care.

[name] is a Post-doctoral Associate at the Miami Project to Cure paralysis. She will be responsible for recruiting and consenting participants. She will schedule participants for visits, and oversee all assessments.

[name], is a Research Associate Professor of Medicine and Director of the Clinical Biochemistry Lab of the DRI. He will assay all bloods for glucose and insulin and provide source data for the study on these analytes.

Other Resources:

As the target recruitment 6 per group, we are confident that this level of enrollment can be satisfied with our planned recruitment methods. The Miami Project maintains a database of persons who have volunteered their participation in research studies. This is a searchable database under the management of [name]., Director of Education. The Miami Project also maintains a database of individuals who have participated in past studies and volunteered additional participation.

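### For Aim 1, section 12 names only main effects; the condition main effect averages in the pre-treatment Day-1 OGTT and so estimates half of the AIH effect

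*Combined protocol and SAP*

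**What the plan says.** Specific Aim 1 (section 3) asks whether four days of AIH "will result in improved glycemic control when compared to a normoxic (SHAM) condition".

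Section 10, item 4, sets the measurements: "On day 1 and day 4 of each treatment series, subjects will undergo a fasted OGTT", and "On day 1, the OGTT will be performed before the treatment and on day 4 it will be performed after the treatment". Glucose AUC and the composite insulin sensitivity index each give one value per OGTT (section 10, item 5). For these outcomes the layout is therefore two conditions by two days within each participant.

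The analysis in section 12 (Data Analysis) reads "We will use a mixed-model ANOVA and a repeated measures design to examine main effects of" test condition and time, with Least Significant Difference tests post hoc and a 0.05 significance level. Nothing in the document names a condition-by-time interaction, a change from Day 1, a Day-1 covariate or a Day-4 comparison. The same section gives the purpose: "We will be using this study to obtain data necessary to compute effect sizes for future work".

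For the Aim 2 outcomes, item 4 says "Each treatment series will be followed by a repeat of the graded exercise tests within 24 hours of the final exposure session". Those outcomes can be compared directly, post-AIH against post-SHAM, so the point is limited to Aim 1.

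**The concern.** Half of the OGTTs labelled AIH are taken before any AIH has been given in that series. Averaging them with the Day-4 tests dilutes the treatment effect and adds half of any chance Day-1 difference between the two series. The time main effect has a different fault: it combines both conditions, so a practice, diet or day-to-day trend common to AIH and SHAM shows up in it as readily as an AIH effect. The two effects that the plan names therefore leave Aim 1 without an estimate.

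What is at stake is the number carried forward. If the condition main effect is reported as the effect of AIH on glycemic control, a later trial would be planned on an effect that is too small. It would be made larger than it needs to be, or a worthwhile effect would be set aside.

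**Working it through.** The documents give no power, effect size, SD or correlation, so there is no stated figure to reproduce.

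**Step 1: what each effect estimates.** Let δ be the AIH effect at Day 4 and τ a Day-1-to-Day-4 trend common to both conditions. Assume equal expected Day-1 values (randomized order) and no carryover. The expected cell means, relative to Day 1, are AIH Day 1 = 0, AIH Day 4 = τ + δ, SHAM Day 1 = 0, SHAM Day 4 = τ.

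- Condition main effect: (0 + τ + δ)/2 − (0 + τ)/2 = δ/2.
- Time main effect: (τ + δ + τ)/2 − 0 = τ + δ/2.
- Condition-by-time interaction: (τ + δ − 0) − (τ − 0) = δ.
- Day-4 contrast: (τ + δ) − τ = δ.

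A simulation of 20,000 subjects with δ = 1 and τ = 0.3 gave 0.494, 0.798, 1.000 and 0.995 for these four in turn.

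**Step 2: assumptions for precision.** Let D1 and D4 be the within-subject AIH-SHAM differences at Day 1 and Day 4, each with SD 1 and with correlation ρ. The effect is in D4 only, with δ = 0.66 (0.6604 unrounded), the size that gives a paired t test 80% power at N=20, two-sided 0.05. Since ρ is unknown, 0, 0.3 and 0.5 are shown. N=20 comes from section 6 ("Total target accrual is N= 20; 10 SCI and 10 CON").

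- Main effect = mean of (D1 + D4)/2: expectation δ/2 = 0.33, per-subject SD √((1+ρ)/2) = 0.707, 0.806, 0.866.
- Interaction = mean of D4 − D1: expectation 0.66, SD √(2(1−ρ)) = 1.414, 1.183, 1.000.
- Adjusted Day-4 difference = intercept of D4 on D1 and sequence, n − 3 df: expectation 0.66.

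Power for the first two comes from the noncentral t with n − 1 df; for the adjusted estimate it comes from simulation.

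| N=20 | ρ=0 | ρ=0.3 | ρ=0.5 |
|---|---|---|---|
| Main effect, raw estimate | 0.33 | 0.33 | 0.33 |
| Main effect, standardized (0.33/SD) | 0.47 | 0.41 | 0.38 |
| Power, main effect | 51% | 41% | 37% |
| Power, interaction | 51% | 66% | 80% |
| Power, adjusted Day-4 difference | 77% | 81% | 87% |
| 95% CI of main effect covers δ | 49% | 59% | 63% |

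The last row follows from the power row. The main effect lies as far below δ as it lies above zero (both δ/2), so its interval misses δ as often as it excludes zero: 100 − 51, 100 − 41 and 100 − 37. The interaction and the adjusted difference cover δ in about 95% of trials.

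Section 22 gives a smaller size ("As the target recruitment 6 per group"). At N=12 the powers at the three ρ are 32%, 25%, 23% (main effect), 32%, 42%, 55% (interaction) and about 49%, 53%, 61% (adjusted).

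**Step 3: the next trial.** The smallest n with 80% paired-t power at the standardized main effect is 38, 49 or 56. On the standardized interaction (0.66/SD = 0.47, 0.56, 0.66) it is 38, 28 or 20, and on the paired Day-4 difference it is 20. If instead the halved raw effect is set against the Day-4 SD, n rises about fourfold. For an assumed true effect of 0.5 SD, (1.96 + 0.84)²/0.5² gives 32, and the same formula with 0.25 gives 126.

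**Step 4: type I error.** With δ = 0, ρ = 0.3 and N=20, simulated rejection rates were 5.0% (main effect), 4.8% (interaction) and 4.9% (adjusted).

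**The case against.** The strongest reply is that the plan leaves the estimate unspecified and does not commit to a wrong one. It does not say that the main effects are the only effects examined. A repeated-measures ANOVA with two crossed factors normally prints the interaction. Since condition and day have two levels each, post hoc tests are informative for AUC and the sensitivity index only if they compare condition-by-day cells, which would include AIH Day 4 against SHAM Day 4. All four OGTTs are collected, so the right difference can always be computed later. This is fair as far as it goes, and the harm is indeed conditional on the main effect being reported as the AIH effect. But printed output is not a pre-specified estimate, the plan does not say which cells the post hoc tests compare, and the two effects it does name do not answer Aim 1.

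The second reply concerns size, and it stands. The factor of one half is exact only on the raw scale. The standardized main effect is 71%, 62% or 58% of 0.66 (0.47, 0.41 and 0.38, taken before rounding). At ρ=0, which holds if all four OGTTs are equally correlated, the interaction has the same power and implies the same next-trial size (38) as the main effect. At ρ=0 the adjusted test (77%) is also slightly below a plain paired Day-4 test (80%). The power and sample-size figures rest on assumed values and illustrate the consequence. The halving does not rest on them.

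**Conclusion.** The concern holds for Aim 1 and should be fixed. Given equal expected Day-1 values and no carryover, the condition main effect estimates δ/2 in outcome units whatever the SD or correlation, and the time main effect is not evidence about AIH. Any carryover of AIH into a later SHAM series would move the condition effect further from δ. The loss of power is conditional: none against the interaction at ρ=0, and 43 points (80% against 37%) at ρ=0.5 and N=20 under the assumed effect. The plan makes no power claim, and type I error is sound. The damage is to the effect size, which is what the study is meant to deliver.

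**What to change.** State in section 12 the test and estimate for each aim.

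- **Aim 1.** Regress the within-subject Day-4 AIH-SHAM difference on the within-subject Day-1 AIH-SHAM difference and on sequence, coded +1/−1 so that the period effect is removed. The AIH effect is the intercept at a Day-1 difference of zero. Do not centre that covariate on its sample mean, because that would undo the adjustment. The condition-by-time interaction is an acceptable alternative.
- **If a mixed model with a random subject effect is preferred,** split the Day-1 value into the subject mean and the within-subject deviation. In a check at ρ=0 and N=20 (1,500 simulated trials; within-subject SD 0.71, between-subject SD 2), entering the raw Day-1 value alone gave under 60% power, against 79% with the split.
- **Aim 2.** Compare post-AIH with post-SHAM directly, and adjust in the same way only if each series has its own rest and exercise test beforehand.
- **Reporting.** Give the AIH-SHAM difference with a 95% CI as the effect size, and do not read the time main effect as an AIH effect. Estimates within SCI and CON may be added as exploratory, with CIs.

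The cost is a few sentences and about 2 degrees of freedom (Day-1 difference and sequence). Visits, data and software stay the same.

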5. Subjects will undergo a 2-hour oral glucose tolerance test using a 75-g oral glucose load (Trutol) ingested over a 5 minute period. Subjects will fast overnight (8 hours) and will be prepared under antiseptic conditions with an indwelling 21g antecubital venous catheter (Jelco) having a multi-sample Luer connector cap, which will be kept patent with sterile physiological (0.9%) saline. Blood samples obtained in vacutainer tubes containing NaF and clot lysis activator will be centrifuged and assayed for glucose and insulin (via Roche auto-analyzer) which we have reported. We will plot glucose concentrations at 0, 30, 60, 90, and 120 minutes and measure area under the curve (AUC) using Graphpad PrismTM software. An additional assessment of whole-body insulin sensitivity will encompass both hepatic and peripheral tissues, which is derived by combining the insulin sensitivity index (ISI) during the oral glucose tolerance test (OGTT) with that obtained during the basal state, the latter of which primarily reflects hepatic insulin sensitivity. This composite 'whole-body ISI' during the OGTT [ISI(composite)] will be calculated as: $1002/[(FPG \times FPI) \times (GMEAN \times IMEAN)]^{0.5}$, where 1002 represents a constant that generates values ranging from 0 to 12, FPG = fasting plasma glucose, FPI = fasting plasma insulin, and GMEAN and IMEAN reflect the 2-hour (75g) OGTT averages for glucose and insulin, respectively. The ISI (composite) has been comprehensively compared against other standardized methods used to determine insulin sensitivity, and is strongly correlated ($r = 0.73$, $p < 0.0001$) with the direct measure of insulin sensitivity derived from the euglycemic insulin clamp.

Data And Specimen Banking

Data Banking

Specimens – General – Whole blood will be taken for the OGTT. Centrifuged plasma will be discarded after assays for insulin and glucose are completed.

Electronic Data – All electronic files are stored on password-protected computers in rooms 1-48 and 1-50 of the Lois Pope Life Center. Computer security is provided by data encryption, firewall protection, and backup on the Miami Project Server.

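### No primary outcome or contrast is named and every test is run at an unadjusted 0.05, so the chance of a false positive is well above 5% and the effect sizes are open to selection

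*Combined protocol and SAP*

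**What the plan says.** Section 3 sets two aims, each a domain and not a measure. Aim 1 asks whether AIH "will result in improved glycemic control when compared to a normoxic (SHAM) condition". Aim 2 asks whether it "will result in a greater reliance on fat as a fuel source at rest and during exercise".

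Section 9 carries the title Study Endpoints but defines only when the study stops: "The study will end after 20 participants have completed all testing".

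Section 10 supplies the measures without ranking them:
- From the OGTT on days 1 and 4: glucose AUC and ISI(composite).
- From the gas-exchange data: total energy expenditure, carbohydrate oxidation and fat oxidation.
- Also collected: lactate and two ratings of perceived exertion.

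Section 12 holds the whole analysis plan. "We will use a mixed-model ANOVA and a repeated measures design to examine main effects of" condition and time; the condition-by-time interaction is not mentioned. Then "Post hoc analyses will use the Least Significant Difference test". The 0.05 level has no exception or split: "Significance for all tests will be set" at that value. The same section says that there are no data on which to base power and that the purpose is to obtain effect sizes for later work.

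**The concern.** When several unranked outcomes are each tested at 0.05, the 5% error rate belongs to each test and not to the study's conclusion. Nothing in the plan stops the outcome, effect or pair of cells that looks best from being presented as the finding.

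This matters even in a study meant only to supply effect sizes. An effect chosen because it was the largest or was significant is biased away from zero, and a later trial sized on it would be too small.

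The missing contrast adds to the problem. The day 1 OGTT is done before treatment, so the main effect of condition averages untreated and treated data and does not isolate the effect that Aim 1 asks about. The interaction would, but it is not named. That leaves cell-by-cell post hoc tests as a plausible route to the treatment claim.

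**Working it through.** The plan states no familywise error rate or power, so there is no figure to reproduce beyond the per-test level of 0.05.

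**Inputs from the protocol.** Per-test level 0.05 (Section 12); 20 participants, each receiving both conditions (Sections 6 and 10); two conditions; two OGTT days (Section 10).

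**Assumptions.** The protocol fixes neither the number of outcomes tested nor their correlation.
- Four outcomes: glucose AUC, ISI(composite), and fat oxidation at rest and in exercise.
- Eight outcomes: these plus carbohydrate oxidation and energy expenditure, each at rest and in exercise.
- Correlation between outcomes: 0 to 0.8.

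**Step 1. Independent tests.** P(at least one false positive) = 1 − 0.95^k.
- k = 2: 9.8%
- k = 4: 18.5%
- k = 8: 33.7%
- k = 13: 48.7%
- k = 14: 51.2%

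**Step 2. Correlated outcomes** (simulation, n = 20, no true effect):

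| Outcomes | Effects counted per outcome | Correlation 0 | Correlation 0.5 | Correlation 0.8 |
|---|---|---|---|---|
| 4 | one contrast | 18% | 16% | 12% |
| 8 | one contrast | 34% | 26% | 16% |
| 4 | condition or interaction | 34% | 29% | 23% |
| 8 | condition or interaction | 56% | 45% | 30% |

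Repeat runs differ by about one percentage point.

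**Step 3. What LSD adds within one outcome.** For a two-level factor, LSD is the same test as the F-test (4.9% simulated), so it adds nothing for AIH versus SHAM or day 1 versus day 4 taken alone. It can add error among the four condition-by-day cells, which form 4 × 3 / 2 = 6 pairs. With n = 20 and correlation 0.6 between cells:
- no F-test required first: 20% (pooled error term) to 21% (separate paired t-tests);
- only after a significant omnibus F-test: 4.9%.

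**Step 4. Bias from selection.** A paired t-test with 19 degrees of freedom needs |t| > 2.093, so any significant standardized paired effect is at least 2.093 / √20 = 0.47. With no true effect, the most favourable of eight outcomes averages 0.15 (correlation 0.8) to 0.34 (correlation 0). One outcome named in advance averages 0.

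**Step 5. After the fix.** One outcome and one contrast per aim gives two tests. At 0.05 each: 1 − 0.95² = 9.8%. At 0.025 each: 1 − 0.975² = 4.9%.

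**The case against.** The strongest defence is the stated purpose. This is a 20-person exploratory study, the aims already name AIH versus SHAM, and strict familywise control in such a study is partly a matter of preference. That lowers the severity. It does not remove the point, because Section 12 still sets a significance threshold for all tests, and selection damages the effect sizes the study is meant to provide.

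A reader might also infer more than the documents support:

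- **That every comparison uses LSD.** It does not. Section 12 tests main effects by mixed-model ANOVA and keeps LSD for post hoc work. Most of the inflation comes from unranked outcomes and effects.
- **That a false positive is more likely than not.** With one contrast per outcome, passing 50% takes 14 independent tests. The outcomes here are related: the oxidation rates and energy expenditure all come from VO2 and VCO2, and AUC and ISI share glucose values. Eight outcomes pass 50% only if several effects per outcome are counted and, for condition and interaction alone, only at low correlation.
- **That SCI and CON cells will be compared pairwise.** Eight cells would give 28 pairs and about 48%, but Section 12 names only condition and time.
- **That lactate and perceived exertion will be tested.** Section 10 says that they are collected. No aim or analysis statement says that they are tested.

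It is fair to say that post hoc tests usually follow a significant F-test, and that gating by the omnibus F-test brings 21% down to about 5%. That protection holds when nothing differs at all. Suppose instead that both conditions shift by an assumed 0.5 SD from day 1 to day 4 and AIH has no effect (cell correlation 0.6). The gate then opens in most runs (93% if any of the effects may open it), and a false AIH-versus-SHAM difference on one of the days appears in about 10%. In about 22% the AIH change is significant and the SHAM change is not, a pattern easily misread as benefit.

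**Conclusion.** The concern holds in a limited form. No primary outcome or contrast is named, and all tests use 0.05 without adjustment. The false-positive chance is about 12% to 19% for four outcomes and 16% to 34% for eight with one contrast each, and higher if several effects per outcome are counted. LSD is a secondary contributor: about 21% or about 5% within one outcome, depending on a gating rule that the plan leaves open. These figures rest on the assumed outcome counts and correlations and on no true effect. The documents do not show that a false positive is probable, only that its chance is well above the nominal level. Given the exploratory purpose, this is a cheap improvement and not a flaw that invalidates the study.

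**What to change.** In Sections 9 and 12:

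1. Name one outcome per aim, for example ISI(composite) or glucose AUC for Aim 1 and resting fat oxidation for Aim 2.
2. Define the contrast. For Aim 1, use the condition-by-time effect: (day 4 − day 1 under AIH) − (day 4 − day 1 under SHAM). For Aim 2, state whether it is a post-treatment difference or a difference in change. Section 8 says that all testing is repeated with the second treatment, while Section 10 describes an exercise test at screening and one after each series. First settle whether a second-period baseline exists.
3. State whether alpha is shared across the two aims (0.05 each or 0.025 each), or label the p-values exploratory.
4. Replace LSD with Holm within any remaining set of pairwise tests, or drop those p-values.
5. Report every other outcome as exploratory, as an estimate with a 95% confidence interval, whatever its p-value.

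The cost is protocol wording only, with no added participants, visits or assays. The downside is that some secondary pairwise results will lose nominal significance.
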